#### 4.3 Screening of Candidate Subjects

- (1) The investigator (attending physician) selects candidate patients based on information available in routine medical practice.
- (2) The investigator, upon determining that a patient is potentially eligible to participate in this study (3.1 and 3.2), shall record on the Patient Screening Form (Appendix) an arbitrary symbol or number that is linkable within the study site. No patient screening forms linkable within the site will be submitted anywhere outside of the facility.
- (3) The investigator shall communicate the information of a potentially eligible candidate on the IC Inquiry Form (Appendix) to the independent enrollment supervisory board (16.6) by email

([contact]).

- (4) For candidates who are not enrolled, record on the Patient Screening Form “did not meet the inclusion criteria,” “declined to participate,” or “other reason.”

[Rationale for the choice of Patient Screening Form]

The Patient Screening Form was selected because it provides the information necessary to identify “did not meet the inclusion criteria,” “declined to participate,” or “other reason” in the process of preparing a flowchart for screening patients to be included in the analysis.

[Rationale for the choice of IC Inquiry Form]

Inquiries to the independent enrollment supervisory board require information that aids the verification of eligibility and the assessment of the justification for obtaining informed consent. Thus, the form gives the investigator the discretion to freely record information. Furthermore, with regard to the exclusion criterion, “presence of a mental illness related to cognitive function (including delirium),” the investigator is to inquire about “the patient’s overall condition (e.g., disease recognition, decision-making ability, relationship with the medical care team, and interest in the clinical trial).”

#### 4.4 Informed Consent

- (1) Inform patients after confirming approval has been granted by the independent enrollment supervisory board to administer informed consent.
- (2) Inform patients as instructed in the Manual for Obtaining Informed Consent (Appendix), with the patient’s right to decide whether to participate or not fully respected
- (3) When presenting information to a patient, pay due attention to the patient’s physical condition.
- (4) The investigator (attending physician) shall use the Written Information (Appendix) to provide an explanation about the present trial to patients who are candidates for inclusion in the study and use the Informed Consent Form (Appendix) to obtain voluntary consent directly from the patient.
- (5) Meanwhile, the investigator shall also obtain the signature of a family member of the patient to signify that the family has also consented to the patient’s inclusion in the trial.
- (6) In cases where no consent could be obtained from a patient and his or her family member, the investigator shall indicate this on the Patient Screening Form.

#### 4.5 Eligibility Verification

- (1) The investigator (attending physician) shall verify the eligibility of participants who gave consent to participate in the study.
- (2) Assess eligibility based on clinical data available on the day of eligibility verification or clinical data obtained within 2 weeks before the eligibility verification.
- (3) In cases where a patient is deemed ineligible, indicate this on the Patient Screening Form.
- (4) In cases where a patient is potentially eligible (3.1 and 3.2), the investigator shall communicate

this to the independent enrollment supervisory board by email promptly once the patient becomes a candidate for informed consent. (4.3 (3)).

#### 4.6 Enrollment

- (1) To enroll a participant, the investigator (attending physician) shall fill out a hard copy of the enrollment form with the required information, which is to be verified by two individuals: the investigator (attending physician) and another clinician.
- (2) The investigator shall enter the eligibility criteria-related information in the data center-provided enrollment form (electronic data capture [EDC]) on a computer and inform the secretariat through its mailing list ([contact]).
- (3) In the present trial, for outpatients, carry out the procedures from informed consent to enrollment on the same day and commence treatment with the study drug on the following day (Day 1).

##### 4.6.1 Enrollment Procedure

The investigator (attending physician) shall enter on the Enrollment Form, the date of enrollment, the name of the study site and a predetermined symbol for the study site, a serial number (participant enrollment number) assigned within the study site, participant's information (date of birth or age, sex, date on which the independent enrollment supervisory board gave approval, date of informed consent, date of treatment commencement, name of the primary cancer diagnosed, date of diagnosis, and Eastern Cooperative Oncology Group Performance Status [ECOG PS]), and the result of eligibility verification (a check list of inclusion and exclusion criteria).

- (1) The investigator (attending physician) shall ask a clinician other than an investigator (attending physician) to verify the information provided on the Enrollment Form.
- (2) The investigator, after the information on the Enrollment Form has been verified, shall verify the allocation number without changing the study drug's serial number that has been distributed in advance to the study site and enter the number on the Enrollment Form.
- (3) The investigator (attending physician) shall ask a clinician other than another investigator (attending physician) to verify the allocation number of the study drug concerned. The individual who verifies the information shall sign and date the verification section of the Enrollment Form.
- (4) The investigator (attending physician) shall enter the allocation number on the Patient Screening Form (Appendix), which is used as a reference table for anonymized numbers within the study site.
- (5) The investigator (attending physician) shall retain the Enrollment Form and the Patient Screening Form, which is used as a reference table for anonymized numbers.

##### 4.6.2 Participant Enrollment Numbers

A participant enrollment number (XX-YY) comprises the following parts.

XX: the study site number

YY: a serial number assigned within a study site to a participant enrolled in the present trial

#### 4.6.3 Random Drug Allocation

- (1) Randomly allocate drugs according to the allocation schedule prepared by the allocation manager (16.9 and 16.10 below).
- (2) Allocate drug numbers so that the ratio of corticosteroid group to placebo group is 1:1.
- (3) Allocation is to be carried out by the variable block randomization method at the pharmacy department of the study drug manager.
- (4) The allocation manager shall supervise the variable block allocation and verify the drug allocation according to the operating procedure for allocation (16.9 and 16.10 below).

#### [Rationale for the choice of variable block allocation]

The present trial is to be conducted in both outpatients receiving home care and inpatients. The wait time during office visits should be minimized as much as possible for PS2/3 terminal-stage patients with advanced cancer-related fatigue. Thus, we chose block allocation, which allows the study drug to be prepared in advance. Given the need to blind the study drug in block allocation, variable block allocation was selected.

#### 4.7 Blinding

##### 4.7.1 Allocation Concealment

The present trial is a placebo-controlled, double-blind, comparative study.

The allocation is carried out by the variable block randomization method based on a written specification for creating allocation schedules prepared by the allocation manager, who keeps the allocation schedule confidential to conceal the allocation.

##### 4.7.2 Ensuring Blindness

- (1) Confirming indistinguishability between the investigational product and placebo  
Before blinding the study drug, the allocation manager shall check the study drug to be allocated to confirm that the investigational product and placebo are indistinguishable.
- (2) Generating and retaining allocation numbers  
The allocation manager shall generate allocation numbers based on the written specification for creating allocation schedules and retain the numbers under seal until the declaration of data lock by the principal investigator (10.4 below) after the completion of data check following the completion of the trial in all patients (10.2 below).
- (3) Review of blindness  
The allocation manager, after the declaration of data lock, shall review the blindness of the study drugs that have been stored in random order as opposed to the enrollment numbers and verify whether the study drugs were allocated based on the allocation schedule (16.9 and 16.10 below).

#### 4.8 Emergency Code Breaking

In the event a participant develops a serious adverse event during the study treatment period that is

life-threatening or requires emergency treatment and the information on whether betamethasone was administered is deemed necessary to make a treatment decision for the participant, the investigator (attending physician) shall follow the following procedures to have the participant's allocation number disclosed.

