## 4 Protocol

### 4.1 Study Design

A multicenter, placebo-controlled, double-blind (attending physicians and patients), randomized, parallel-group comparative study.

The present trial is a clinical trial that compares alleviation of fatigue (systemic conditions), an approved indication of betamethasone, between betamethasone- and placebo-treated groups of performance status 2 or 3 (PS2/3) terminal-stage patients with advanced cancer-related fatigue. The study treatment period for individual participants begins on the day (Day 1) after the enrollment-baseline date (Day 0) and ends at study treatment discontinuation or completion (Day 7). During the trial period, the randomly allocated study treatment (with steroid or placebo) will be administered to all participants under blinded conditions. Furthermore, in the present trial, an outcome survey on death of individual participants after the end of their study treatment will be conducted.

[Rationales for the choice of study design]

(1) The multicenter design of the present trial was chosen to 1) increase the likelihood of obtaining generalized findings by recruiting diverse study sites, given the impacts from factors intrinsic to a particular study site, and 2) ensure a sufficient number of enrolled patients.

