(2) The placebo-controlled design was chosen for the following reasons. 1) The study intends to provide patients appropriate palliative care regardless of whether intervention with a steroid is given and to determine the efficacy of the steroid's effect. Thus, to accurately assess the steroid's effect, placebo is needed as a comparator. The appropriate palliative care mentioned above refers to alleviation (or spiritual care in some facilities) of various distressing physical symptoms (e.g., treatment for dyspnea, in the case of lung cancer, or for nausea, vomiting, and constipation/diarrhea, in the case of gastrointestinal cancer) related to certain types of incipient cancer; pain, insomnia, and other physical symptoms associated with many end-stage cancers; and psychological and social issues. 2) Given that a placebo has the potential to provide a certain effect (placebo effect) in terms of alleviating fatigue, a subjective symptom, it is necessary to assess whether treatment with a steroid in the intervention group provides an added effect over and above the placebo effect. 3) We had the following discussion with collaborating physicians involved in palliative care about whether it is ethical to use a placebo control fatigue in PS2/3 terminal-stage patients with advanced cancer-related fatigue. Based on empirical knowledge derived from clinical practice, unlike pain therapy and other treatments that must be rendered promptly, no standard therapeutic intervention has yet been established to improve the quality of life (QOL) of fatigued patients, and the time to commence such a therapy may vary by about a week in normal clinical practice. Unlike therapies to treat pain, nausea, and dyspnea, which must be rendered promptly based on a specified procedure to determine when to commence treatment in clinical practice, a delay of about a week in giving the placebo group treatment with a steroid for fatigue in the present trial is not considered a material deviation from current clinical practice.

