#### 4.8.1 Procedures for Emergency Disclosure of Allocation Numbers

- (1) In the event the conditions described above for disclosure of allocation numbers are deemed met, the investigator (attending physician) shall take actions according to one of the two procedures below.
- (2) Procedure 1: The investigator (attending physician) shall unseal the envelope marked "Procedure for Emergency Code Breaking of Allocation Numbers" that has been prepared in advance by the head of the independent data monitoring board and sealed and distributed by the secretariat, and follow the instructions provided therein.
- (3) Procedure 2: The investigator (attending physician) shall contact the secretariat by phone and follow the procedures as instructed.
- (4) When contacted by the investigator (attending physician) per Procedure 2, if the secretariat alone is unable to take actions in response, he/she shall promptly contact the allocation manager to confirm the study drug group and contact the investigator (attending physician) by phone or email.

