## 5 Adverse Events Assessment and Reporting

### 5.1 Definition of Adverse Event

In the present trial, all adverse events occurring during the study treatment are subject to evaluation. An adverse event for which a causal relationship to the study treatment cannot be ruled out is defined as an adverse drug reaction (ADR) to the study treatment. Of the ADRs occurring in the steroid group, those described in the package insert of Betamethasone Tablets (Appendix) are defined as known ADRs, and those not described in the package insert or those described but inconsistent in nature or severity are defined as unknown ADRs (unexpected ADRs).

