## 5.4 Adverse Events Reporting

In the present trial, upon occurrence of a serious adverse event during the study treatment period, the treatment approach for the participant concerned shall be reviewed, and, if obtaining the study drug

information is deemed necessary, communications shall be appropriately carried out according to the procedure established at each study site.

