#### 5.4.2 Emergency Reporting

- (1) In the present trial, serious adverse events that meet the following description are subject to the emergency reporting requirement: any event occurring in the study treatment period that is life-threatening, requires emergency intervention, and for which information on whether the administration of betamethasone should be allowed is deemed necessary to review the treatment approach for the participant concerned.
- (2) Upon occurrence of an adverse event that is deemed "life-threatening and requiring emergency intervention as well as information on whether the administration of betamethasone should be allowed in order to review the treatment approach," the attending physician shall promptly notify the investigator. In the event the investigator cannot be contacted, the physician shall assume the responsibility of the investigator.
- (3) If an event is deemed "life-threatening and requiring emergency intervention as well as

information on whether the administration of betamethasone should be allowed in order to review the treatment approach,” the investigator shall report the event immediately to the director of the hospital facility.

- (4) The investigator shall follow the procedures provided in 4.8 for emergency code breaking and reporting.
- (5) The investigator (attending physician) shall record what transpired that led to the disclosure of the study drug allocation number and the disclosed information following Procedure 1 of 4.8 (emergency code breaking) or Procedure 2 (contacting the secretariat) on the Emergency Allocation Number Code Breaking Request Reporting Form, send it by email attachment or facsimile transmittal to the secretariat within 72 hours from the day of such a request, and retain the allocation number. The investigator shall also retain the sent file.

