#### 16.10 Allocation Manager

The allocation manager shall create specifications for preparing allocation schedules, generate an allocation schedule based on the specifications, and keep it under seal until the data lock declaration. Furthermore, the allocation manager shall also create an operating procedure for allocation and verify whether the study drug was properly allocated based on the operating procedure. In addition, the allocation manager shall review the blinding after the data lock declaration.

[name]	Kyoto University Health Service
[name]	Kyoto University Health Service

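### Emergency code breaking is tied to events that develop during the treatment period, so the protocol writes no route to disclosure for an emergency that begins after it

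*Protocol*

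**What the plan says.** Section 4.8 makes disclosure available "In the event a participant develops a serious adverse event during the study treatment period that is" life-threatening or calls for emergency treatment, provided that knowing whether betamethasone was given is needed to decide treatment. Section 4.8.1(1) then admits the investigator to the sealed envelope (Procedure 1) or the telephone call to the secretariat (Procedure 2) "In the event the conditions described above for disclosure of allocation numbers are deemed met".

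The time limit appears in two further places. Section 5.4 provides for obtaining study drug information where, "upon occurrence of a serious adverse event during the study treatment period, the treatment approach for the participant concerned shall be reviewed". Section 5.4.2(1) defines the events for emergency reporting as "any event occurring in the study treatment period that is life-threatening, requires emergency intervention" and for which betamethasone information is needed.

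Section 4.1 states that the treatment period "ends at study treatment discontinuation or completion (Day 7"). Sections 4.7.2(2) and 16.10 govern everything else: the allocation manager is to "keep it under seal until the data lock declaration". Section 16.5(3) adds that the independent data monitoring board decides on the secretariat's requests for emergency code breaking, and it names no time limit.

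**The concern.** A life-threatening event that starts on the day after the last capsule can meet every condition in section 4.8 except the timing. The treating physician may need to know whether the participant has just had a week of betamethasone. A site that follows the text exactly finds no procedure that it may use.

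The protocol itself treats steroid exposure as relevant to acute risk. Section 5.5.1 lists hyperglycemia and gastrointestinal hemorrhage among reported events, although particularly with long-term use. Section 3.2 excludes apparent infection and drug-treated peptic ulcer on safety grounds. The placebo rationale in section 4.1 speaks of "a delay of about a week in giving the placebo group treatment with a steroid for fatigue", so steroid use after the placebo week is at least contemplated.

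What is at stake is participant safety and a workable blinding procedure. The estimate, the test and the sample size are not affected.

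**Working it through.** The plan gives no statistical figure on this point, so the check sets the provisions side by side.

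1. **Condition.** Sections 4.8, 5.4 and 5.4.2(1) all require that the event falls in the study treatment period. Three places agree, so this is a stated rule and not a slip in one sentence.
2. **Access.** Section 4.8.1(1) admits the investigator to either procedure only when the section 4.8 conditions are judged to be met. The envelope and the telephone line therefore share the limit.
3. **End of the period.** Section 4.1 gives discontinuation or Day 7. Three cases follow:
   - An event that starts on Day 6 and worsens on Day 9 developed during treatment and is covered.
   - A new event on Day 8 in a participant who completed treatment is not covered.
   - A new event on Day 4 in a participant who stopped on Day 3 is not covered. Section 4.12.1(1) makes an adverse event a ground for stopping, so this case is realistic.
4. **Default.** Sections 4.7.2(2), 4.14(3) and 16.10 hold the allocation until the data lock declaration.
5. **Other route.** Section 16.5(3) concerns a request made by the secretariat. It gives the investigator no way to start one, and section 4.8.1 contains no step that sends a late request to the board. It does not widen the section 4.8 conditions.
6. **Calendar length.** Under section 15.1 the study is complete at the death of all participants or 16 weeks after the last enrollment, whichever is earlier. For the last participant enrolled this is at most 16 × 7 = 112 days from enrollment, or 112 − 7 = 105 days after Day 7, plus the data check. This is an upper limit on calendar time, not time at risk: the rationale in section 3.1 places participants in the last 1 to 2 months before expected death.
7. **Effect on the endpoint if the limit goes.** For a participant who completes treatment, the fatigue score is recorded on Day 7 (sections 4.13.1 and 6.1), so later disclosure cannot change it. For an early discontinuer, the questionnaires are filled in after stopping (sections 4.10.6(4), 4.12.2 and 4.17.3), so disclosure could come first.
8. **Mismatch in the conditions.** Section 4.8 asks for a life-threatening event or one needing emergency treatment, and for information on whether betamethasone was administered. Section 5.4.2 asks for both features together, and for information on whether betamethasone should be allowed. No single set of conditions exists at present.

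**The case against.** The strongest reply is that the protocol forbids nothing. Section 4.8 tells the investigator what to do when its conditions are met and does not say that disclosure is barred otherwise. Procedure 2 lets the secretariat give instructions and go to the allocation manager, so the seal is not absolute. Section 16.5(3) has no time limit. The envelope instructions, the serious adverse event flow chart and the site procedures are not at hand and may say more. This stands in part: the supportable statement is that the protocol as shown writes no route, not that disclosure is prohibited. It does not remove the point, because section 4.8.1(1) opens both procedures only on the section 4.8 conditions, and a physician in an emergency should not have to infer permission.

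A second reply is that section 5.1 limits the scope to treatment, since "all adverse events occurring during the study treatment are subject to evaluation". That sets what is evaluated and reported. It does not settle whether a treating physician can obtain the allocation.

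Two stronger readings are tempting and are not supported:

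- A reader might count a window of several years, from the first enrollment through the three-year enrollment period to data lock. Given the expected survival in section 3.1, most early participants would have died long before, and the documents do not say how long one week of exposure matters.
- A reader might say that the limit protects nothing in the primary endpoint. That is true for those who complete Day 7 and false for early discontinuers, whose assessment follows stopping. For some outpatients the performance status rating can also fall after Day 7 (section 4.16(3)), and survival is followed later (section 6.2.1(3)).

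The placebo rationale in section 4.1 is only weak support. It argues that a week's delay is acceptable and says nothing about emergencies or about a need for the allocation.

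**Conclusion.** The point holds as a gap in a stated rule. The protocol gives the investigator no written route to disclosure for an emergency that begins after the treatment period, including soon after early discontinuation. It applies to every one of the up to 210 participants once treatment stops, and it matters most in the days just after the last dose. The documents give neither the number of such emergencies nor the duration of relevance, so neither is estimated here.

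The conclusion assumes that the unseen envelope instructions and appendices do not override the conditions in sections 4.8 and 4.8.1(1). It is worth correcting because the change is small and uses procedures that already exist.

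**What to change.** Remove the treatment-period limit as a condition for code breaking in sections 4.8, 5.4 and 5.4.2(1). One form is to make disclosure available from the first dose until the end of the participant's follow-up. Align section 16.5(3) with this, stating how a request reaches the board and what the board decides.

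Keep the emergency condition, the requirement that the allocation is needed for a treatment decision, disclosure for the one participant only, and the record required by section 5.4.2(5). In the same edit, reconcile sections 4.8 and 5.4.2 so that one set of conditions and one question about betamethasone apply throughout. The sponsor must settle which. Make clear that the adverse event scope in section 5.1 does not govern access to the allocation.

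The cost is wording in a few sections and a few more unblinded participants. For those who complete Day 7 the primary endpoint is already recorded. For early discontinuers, have the discontinuation questionnaires completed before disclosure where the emergency allows, and record each case in which disclosure came first.
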